7.5 Early Termination Visit

If participants develop new / worsening symptoms of coronavirus, they will be directed to their healthcare provider and/or local public health authority for clinical care. We will follow up of hospitalized patients for resolution of their SAE for up to 90 days to assess their final outcome. Participants will be sent the Hospitalization eCRF 14 days after hospitalization is reported with repeats in 14 day intervals until the participant is discharged from the hospital.

7.6 Unscheduled / Sick Visit

Subjects will be provided a central email contact: [contact] as a contact point for questions or concerns. This email will forward to an on-call study physician who will call the participant to resolve their concerns.

8 STUDY PROCEDURES/EVALUATIONS

8.1 Clinical Evaluations

Clinical evaluations are by self-report.

8.2 Laboratory Evaluations

SARS-COV-2 positivity is by self-report. Informed consent asks for access to medical records.

Follow up PCR testing within 14 days is asked on followed questionnaires. Pending test results at 14 days or during hospitalization will be queried for final results with repeat survey sent at day 28.

Informed consent will request permission to contact local public health authorities or their medical provider in the event of lost to follow up or COVID19 disease.

There is no incentive to be dishonest, and we believe healthcare workers in particular will take their responsibilities seriously.

An optional dried blood spot collection will be offered at day 14. At time of informed consent, participants may opt into this collection. The dried blood spots will be used for future serology testing. Participants who opt into this testing will be mailed: i) instructions; ii) Whatman filter paper for dried blood spot collection; iii) one time use lancet; iv) return envelope.

Participants who have entered the trial prior to dried blood spot being offered and are <90 days from study entry will be contact with the option for dried blood spot testing of their antibody serology.

9 ASSESSMENT OF SAFETY

9.1 Specification of Safety Parameters

Hydroxychloroquine has a track record of safety since its FDA-approval in 1955. As an already, FDA-approved medicine, this trial is designed as a pragmatic trial in the setting of a public health emergency.

9.2 Methods and Timing for Assessing, Recording, and Analyzing Safety Parameters

9.2.1 Adverse Events

Hydroxychloroquine has an excellent safety track record, being first FDA-approved in 1955. Adverse events will not be captured, unless they result in hospitalization. See Serious Adverse Events below.

Expected adverse events would include normal events within the general population as well COVID19-related disease events which may include need for hospitalization, pneumonia, respiratory failure, sepsis, and death.

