3.2.2 Secondary Outcome Measures

- Incidence of hospitalization or death
- Incidence of confirmed SARS-CoV-2 detection
- Incidence of symptoms compatible with COVID-19 (possible disease)
- Incidence of all-cause study medicine discontinuation or withdrawal
- Incidence of adverse reactions
- Symptom severity on day 5 or 14 via visual analog scale
- Ordinal Scale of COVID-19 Disease Severity at day 14 (among those who are symptomatic at trial entry)
 - Illness without hospitalization
 - Hospitalization (or post-hospital discharge)
 - Hospitalization with ICU stay or Death

Assessment of outcome measures will be primarily by self-report. As necessary, COVID19 disease will be verified from public health records, medical records, or death certificates. The primary endpoints are different for the two cohorts (those who are asymptomatic with known exposure; or those who are symptomatic at trial entry), and analyses will be done separately for the two cohorts.

The primary analysis will use PCR+ confirmed disease. However if the absence of sufficient testing supplies continues then outpatients will not be offered SARS-CoV-2 testing unless they are sick enough to be hospitalized. In that case an alternate a priori planned analysis will define incident COVID19 disease as a composite of SARS-CoV-2 PCR+ confirmed result OR symptomatic disease (i.e. possible) COVID-19 in those without testing.

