7.3 Follow-up

Day 1 Virtual visit

- Verify receipt of study medicine
- Clinical status check-in
 - Participant starts study medicine (4 tabs), then 3 tabs in 6-8 hours, then 3 tabs daily.
- Query for SARS-CoV-2 testing
- Query for symptom status (0-10 visual analog scale of symptom severity)
- Query for hospitalization or SAEs
- Query for medication-related side effects / AEs

Day 3 Virtual visit

- Query for symptom status (0-10 visual analog scale of symptom severity)
- Query for hospitalization or SAEs
- Query for medication-related side effects / AEs

Day 5 Virtual visit

- Query for symptom status (0-10 visual analog scale of symptom severity)
- Assessment of adherence by self-report
- Completion of study medicine, which has a ~7 day half-life
- Query for study medicine side effects since enrollment
- Query for SARS-CoV-2 testing
- Query for hospitalization or SAEs

Day 10 Virtual visit

- Query for symptom status (0-10 visual analog scale of symptom severity)
- Query for SARS-CoV-2 testing

- Query for SARS-CoV-2 testing
- Query for hospitalization or SAEs

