9.3 Reporting Procedures

9.3.1 Serious Adverse Events

An AE or suspected adverse reaction is considered a serious adverse event (SAE) if it results in any of the following outcomes:

- Death
- Life-threatening adverse event ^(as below)
- Hospitalization
- Persistent or significant incapacity or substantial disruption of the ability to conduct normal life functions, or
- Congenital anomaly/birth defect.
- Important medical events that may not result in death, but are life-threatening, or require hospitalizations may be considered serious when, based upon appropriate medical judgment they may jeopardize the patient or subject and may require medical or surgical intervention to prevent one of the outcomes listed in this definition.

Examples of such medical events include allergic bronchospasm requiring intensive treatment in an emergency room or at home, blood dyscrasias or convulsions that do not result in inpatient hospitalization, or the development of drug dependency or drug abuse.

Life-threatening adverse events: An AE is considered “life-threatening” if, in the view of either the site principal investigator or sponsor, its occurrence places the patient or subject at immediate risk of death. It does not include an AE that, had it occurred in a more severe form, might have caused death. For life threatening AEs, subjects would be recommended /expected to be hospitalized.

Based on the known safety track record of hydroxychloroquine, this pragmatic protocol will focus on death, life-threatening AEs, and hospitalizations. Incapacity / permanent disability is a possibility with COVID19, but this is not associated with hydroxychloroquine. In the event of incapacity, the subject would be expected to be hospitalized.

Hydroxychloroquine and chloroquine are not known to cause teratogenic events and are viewed as safe in pregnancy, especially with short term use. With this trial’s sample size, this will not further delineate this risk. COVID19 disease may indeed be teratogenic. For women who are pregnant, we will ask to follow them through the end of their pregnancy, and they will be sent a follow up eCRF at 1 month post-partum based on their reported estimated date of delivery as provided at the day 14 study visit.

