Thus, the hospitalization or death secondary endpoint will capture relevant SAEs. For those with ongoing hospitalization at the day 14 study visit, participants will be queried in 14 day intervals with the hospital eCRF to assess their final clinical outcome.

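### Section 9.2.1 says adverse events are not captured without hospitalisation, which contradicts a listed secondary outcome and the survey schedule and leaves the status of some non-hospitalised serious events unclear

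*Combined protocol and SAP*

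**What the plan says.** Section 9.2 governs how safety data are assessed, recorded and analysed. Within it, section 9.2.1 sets the capture rule, "Adverse events will not be captured, unless they result in hospitalization", and refers the reader on to the SAE section.

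Three other places bear on this:

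- **Outcomes.** Section 3.2.2 lists "Incidence of adverse reactions" on its own line, separate from hospitalisation or death. The Summary's list of secondary endpoints has no such entry.
- **Schedule.** Section 7.3 includes "Query for medication-related side effects / AEs" on Days 1 and 3 and "Query for study medicine side effects since enrollment" on Day 5. Section 7.4 repeats the Day 5 item on Day 14. A separate item about hospitalisation or SAEs appears at every visit.
- **SAE definition.** Section 9.3.1 begins: "An AE or suspected adverse reaction is considered a serious adverse event (SAE) if it results in any of the following outcomes". Hospitalisation is one outcome among several. Among its examples of important medical events are "allergic bronchospasm requiring intensive treatment in an emergency room or at home, blood dyscrasias or convulsions that do not result in inpatient hospitalization". The section then narrows the protocol's focus to deaths, life-threatening events and hospitalisations, and concludes: "Thus, the hospitalization or death secondary endpoint will capture relevant SAEs".

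**The concern.** The section that should define safety recording disclaims data that the outcome list needs and the surveys collect. Someone building the database or the safety tables from section 9 would have grounds to treat the side-effect answers as outside the trial's safety data. Someone working from sections 3 and 7 would do the opposite. At stake is whether a named outcome, tolerability by arm, is reported at all, and whether a serious event that did not lead to admission has a defined status. The second question is not remote: bronchospasm, blood dyscrasias and convulsions appear both among the 9.3.1 examples and among the potential adverse effects of hydroxychloroquine in section 2.3.1.

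**Working it through.** No arithmetic applies, because the documents give no adverse event rates. The check sets the current text side by side.

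**1. Rule against outcome.** Section 9.2.1 makes capture conditional on hospitalisation. Section 3.2.2 names incidence of adverse reactions without that condition and lists hospitalisation or death separately, so the two are meant to be different outcomes. If only adverse events leading to admission were recorded, the adverse reaction outcome would shrink to a subset of hospitalisations. The two statements cannot both be followed.

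**2. Rule against schedule** (sections 7.3 and 7.4).

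| Visit | Side effects or AEs asked | Hospitalisation or SAEs asked |
|---|---|---|
| Day 1 | yes | yes |
| Day 3 | yes | yes |
| Day 5 | yes | yes |
| Day 10 | no | yes |
| Day 14 | yes | yes |

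Side effects are asked at 4 of 5 visits and SAEs at 5 of 5, of all participants whether or not they were admitted. The schedule therefore collects what 9.2.1 says is not captured.

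**3. Analysis.** SAP II.a presents secondary incidence outcomes as proportions and compares them between arms with Fisher's exact test. Protocol section 11.4 also applies Fisher's test to secondary endpoints. Neither names adverse reactions, but as an incidence outcome in 3.2.2 it falls within both. What is missing is a consistent statement that the data are recorded, not an analysis method.

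**4. Rule against SAE definition.** Taking the categories in 9.3.1 in turn:

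- *Death:* outside the literal 9.2.1 rule if it occurs without admission, but covered by 9.2.3 and by the hospitalisation-or-death endpoint.
- *Hospitalisation:* covered.
- *Life-threatening event or incapacity:* 9.3.1 expects these participants to be admitted. If one is not, no route is described other than the SAE survey item.
- *Congenital anomaly:* covered by the pregnancy follow-up in 7.4, 9.3.1 and 9.3.3.
- *Important medical events:* the lead-in refers to events that are life-threatening or require hospitalisation, but the examples go further and expressly include "blood dyscrasias or convulsions that do not result in inpatient hospitalization". The hospitalisation-or-death endpoint does not contain these. The SAE survey item can pick them up, but 9.2.1 and the closing sentence of 9.3.1 do not say what happens to them afterwards.

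Steps 1 and 2 are direct contradictions. Step 4 leaves a smaller gap, confined mainly to the last category and to life-threatening or incapacitating events that are not admitted.

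**The case against.** The best defence is that 9.2.1 is one ill-fitting sentence in a plan that otherwise works. The surveys ask about side effects, each visit has an SAE item, and the SAP supplies a comparison by arm. Section 9.2.1 sends the reader straight to the SAE section, where 9.3.1 openly narrows the focus on pragmatic grounds and explains why it expects the gravest events to be admitted.

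Much of this stands, and it rules out three stronger readings that a reader might infer:

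- *That every adverse event without admission would be lost.* This applies 9.2.1 alone and ignores the schedule that contradicts it. The documents do not show which would prevail in practice.
- *That the DSMB would judge safety on hospitalisations alone.* Nothing says so. Section 11.3 has the board look at safety trends, section 9.5 defers to a charter not included here, and deaths and all-cause discontinuation of study medicine are also listed outcomes.
- *That participants are unmonitored.* The documents provide optional daily EKG monitoring, an on-call study physician (7.6) and an independent medical monitor for SUSARs (9.3.2). SUSAR reporting is not restricted to hospitalised events.

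The defence does not remove the contradiction. That 9.2.1 is leftover wording is a guess, and it is the sentence in force. The narrowing in 9.3.1 concerns SAEs and does nothing for the adverse reaction outcome. Even there the narrowed list includes life-threatening events, so it is wider than the 9.2.1 rule, and it rests on an expectation of admission without saying how an event is handled when admission does not follow.

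**Conclusion.** The contradiction between 9.2.1 and sections 3.2.2, 7.3 and 7.4 is established on the current text, and the Summary's endpoint list differs from 3.2.2 on the same point. Read literally, 9.2.1 would leave one listed secondary outcome without data that the surveys collect. The SAE inconsistency is real but lesser: 9.3.1 explains most of the narrowing and leaves unclear the status of non-hospitalised events that it counts as serious itself.

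The number of events affected is unknown. Primary endpoints, sample size, error rates and efficacy analyses are unaffected. The conclusion assumes that the survey side-effect items are the intended source for the adverse reaction outcome, which the documents imply but do not state. Because collection and comparison are already planned, this is a correction that should be made, not a critical defect.

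**What to change.** 1. **Section 9.2.1.** Replace the capture sentence with a statement that side effects reported on the Day 1, 3, 5 and 14 surveys are recorded, tabulated by arm as the secondary outcome in 3.2.2, and provided to the DSMB.
2. **Summary.** Add incidence of adverse reactions to the secondary endpoints so that the list matches 3.2.2.
3. **Closing sentence of 9.3.1.** Amend it so that non-hospitalised events that meet the 9.3.1 definition, and are reported through the existing SAE survey item, are recorded and reported alongside hospitalisations and deaths.

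The cost is protocol wording and the work of tabulating answers already requested. No new survey item or visit is needed, and SAP II.a already supplies the comparison.

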9.2.2 Reactogenicity (for Vaccine Studies and Some Therapeutic Trials)

Not applicable

9.2.3 Serious Adverse Events (SAEs)

Hospitalization or death are protocol-defined endpoints.

SAEs (e.g. hospitalizations) will be followed for up to 90 days to assess final outcome.

9.2.4 Procedures to be Followed in the Event of Abnormal Laboratory Test Values or Abnormal Clinical Findings

Not applicable

9.3 Reporting Procedures

9.3.1 Serious Adverse Events

An AE or suspected adverse reaction is considered a serious adverse event (SAE) if it results in any of the following outcomes:

- Death
- Life-threatening adverse event ^(as below)
- Hospitalization
- Persistent or significant incapacity or substantial disruption of the ability to conduct normal life functions, or
- Congenital anomaly/birth defect.
- Important medical events that may not result in death, but are life-threatening, or require hospitalizations may be considered serious when, based upon appropriate medical judgment they may jeopardize the patient or subject and may require medical or surgical intervention to prevent one of the outcomes listed in this definition.

Examples of such medical events include allergic bronchospasm requiring intensive treatment in an emergency room or at home, blood dyscrasias or convulsions that do not result in inpatient hospitalization, or the development of drug dependency or drug abuse.

Life-threatening adverse events: An AE is considered “life-threatening” if, in the view of either the site principal investigator or sponsor, its occurrence places the patient or subject at immediate risk of death. It does not include an AE that, had it occurred in a more severe form, might have caused death. For life threatening AEs, subjects would be recommended /expected to be hospitalized.

Based on the known safety track record of hydroxychloroquine, this pragmatic protocol will focus on death, life-threatening AEs, and hospitalizations. Incapacity / permanent disability is a possibility with COVID19, but this is not associated with hydroxychloroquine. In the event of incapacity, the subject would be expected to be hospitalized.

Hydroxychloroquine and chloroquine are not known to cause teratogenic events and are viewed as safe in pregnancy, especially with short term use. With this trial’s sample size, this will not further delineate this risk. COVID19 disease may indeed be teratogenic. For women who are pregnant, we will ask to follow them through the end of their pregnancy, and they will be sent a follow up eCRF at 1 month post-partum based on their reported estimated date of delivery as provided at the day 14 study visit.

Thus, the hospitalization or death secondary endpoint will capture relevant SAEs. For those with ongoing hospitalization at the day 14 study visit, participants will be queried in 14 day intervals with the hospital eCRF to assess their final clinical outcome.

9.3.2 Regulatory Reporting

As hydroxychloroquine is an FDA-approved medicine being used at standard dosing, reporting to regulatory authorities will occur in summary format after each DSMB reports and at a frequency of at least annually.

Serious unexpected suspected adverse reactions (SUSARs) which are not expected with COVID-19 nor listed in the FDA package insert will be reported to the IRB. Those SUSARS which are deemed by an independent medical monitor to be related to the study medicine will be reported to the FDA and IRB.

9.3.3 Reporting of Pregnancy

Chloroquine and hydroxychloroquine are not known to be teratogenic. Chloroquine and hydroxychloroquine can accumulate in neonatal eyes. Conversely, the risk of severe COVID-19 infection is unknown, but likely is a heightened risk in pregnant women. The CDC states, "We do not have information on adverse pregnancy outcomes in pregnant women with COVID-19. Pregnancy loss, including miscarriage and stillbirth, has been observed in cases of infection with other related coronaviruses (SARS-CoV and MERS-CoV) during pregnancy. High fevers during the first trimester of pregnancy can increase the risk of certain birth defects."

Thus, the risk/benefit would favor the enrollment of women who may be or are pregnant, so as to not discriminate against pregnant women.

For women who are pregnant, we will ask to have follow through the end of their pregnancy to assess outcome of the pregnancy via a brief survey.

9.4 Type and Duration of Follow-up of Subjects after Adverse Events

Participants who are hospitalized for COVID-19 or SAEs will have up to 90 day follow up conducted to assess their final outcome. Management will be as per the participant's local healthcare provider.

9.5 Safety Oversight (DSMB)

A data and safety monitoring board (DSMB) will oversee the trial. The quorum will include three members and a biostatistician. The PI will be a non-voting observer, providing input as requested. See the DSMB charter for more details.

10 CLINICAL MONITORING

Clinical site monitoring is conducted to ensure that the rights and well-being of trial subjects are protected and that the reported trial data are accurate, complete, and verifiable. Clinical monitoring also ensures that conduct of the trial is in compliance with the currently approved protocol/ amendment(s), ICH, GCP, and with applicable regulatory requirement(s) and Sponsor requirements. Clinical monitoring will also verify that any critical study procedures are completed following specific instructions. Monitoring will be the responsibility of the University of Minnesota.

The automated logic of the REDCap database system will enable complete records. All data are by self report.

11 STATISTICAL CONSIDERATIONS

11.1 Study Hypotheses

We hypothesize that hydroxychloroquine is superior to placebo for preventing progression to COVID-19 disease among those who are asymptomatic.

We hypothesize that hydroxychloroquine is superior to placebo for preventing progression among those with symptomatic mild COVID19 disease preventing hospitalization/death.

11.2 Sample Size Considerations

Two cohorts of 1500 subjects each:

- 1) Asymptomatic persons exposed to COVID-19 disease (750 in placebo, 750 in intervention);
- 2) Symptomatic outpatient COVID-19 disease (750 in placebo, 750 in intervention).

Assuming 90% power, a two-sided alpha = 0.05 and loss to follow-up up to 20%, for each cohort the planned sample size is 750 participants per arm based on the following assumptions:

- 10% transmission rate from COVID-19 cases to close contacts
- For those with symptomatic illness the proportions at day 14 in the placebo group are 90%, 8% and 2%, respectively for illness without hospitalization, hospitalization with ICU stay or death, and hospitalization with an ICU stay or death.

The estimated transmission rates are uncertain. Table 1 below (for the asymptomatic cohort with exposure) shows that we are well powered to detect even a smaller (40%) relative reduction in the incidence of COVID 19 with 80% power for transmission rates of at least 10% with placebo. Table 2 (for the symptomatic group) shows that we are well powered to detect a common odds ratio of 0.6-0.75 under the assumption that the control proportions for illness without hospitalization, hospitalization without ICU stay or death and hospitalization with ICU stay or death are 90%, 8% and 2%, respectively.

Table 1. Sample Size Table for Asymptomatic Participants (Healthcare worker or household contact) With Exposure

Estimated transmission rate with placebo	Estimated transmission rate with drug	Percent relative reduction in transmission rate	Sample size (per arm) with 90% power	Sample size (per arm) with 80% power
10%	5%	50%	621	474
	6%	40%	1014	771
12%	6%	50%	509	389
	7.2%	40%	831	632
15%	7.5%	50%	398	304
	9%	40%	648	493

Table 2. Sample size table for participants with symptomatic disease, assuming that the control proportions are 90% illness with no hospitalization, 8% hospitalization with no ICU stay or death and 2% hospitalization with ICU stay or death.

Log Odds Ratio	Odds Ratio	Sample size (per group) with 90% power	Sample size (per group) with 80% power
0.60	1.82	805	601
0.65	1.91	697	521
0.70	2.01	610	456
0.75	2.12	539	403

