
Statistical Assumptions
	
 • 10% attack rate for close contacts (or 10% progression of disease to hospitalization among those symptomatic at entry) • Comparison of Proportions by Fisher’s Exact test for disease incidence; • Comparison of ordinal scale of disease severity by proportional odds model • N=621 sample per arm has 90% power to detect a 50% relative risk reduction (i.e. $\leq 5.0\%$) in disease incidence or 50% decrease in the ordinal disease severity (to $\leq 4.25\%$ disease incidence and $\leq 1\%$ hospitalization). • 20% dropouts, inflates sample size to n=750 per arm

Schematic of Study Design:

If hospitalization occurs, this SAE will be followed for up to 90 days

For participants who develop symptomatic disease, they will be followed for up to 90 days to assess final outcome status in the event of hospitalization.

Stratification is based on symptom status at baseline

1. 1500 asymptomatic healthcare workers or household contacts exposed to COVID-19
2. 1500 symptomatic COVID-19 outpatients

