11.4 Final Analysis Plan

Primary outcome analyses (intention to treat):

Asymptomatic Cohort Primary Analysis:

Those with asymptomatic exposure: Incidence of COVID 19 disease by day 14 will be assessed via Fisher's Exact Test.

Symptomatic Cohort Primary Analysis:

Those with symptomatic disease at study entry: For a summary metric of the change in symptom severity over 14 days, a longitudinal change over time repeated measures mixed-regression model will estimate the treatment effect by study arm. Subjects without symptoms are coded as a zero severity. Persons hospitalized or dead are coded as 10 severity.

Participants who become symptomatic with COVID19 on Day 1 before receiving the study medicine will be described with the symptomatic cohort.

Secondary Analyses:

For the asymptomatic with exposure cohort, the primary analysis (intention to treat) will be repeated for participants who received at least one dose of the study medicine.

- Secondary endpoints will be assessed via Fisher's Exact test and median (with interquartile ranges) as appropriate.
- Those with symptomatic disease at study entry: Proportional odds models will be used to assess the ordinal scale for disease severity at day 14 (illness without hospitalization, hospitalization without ICU stay or death, or hospitalization with ICU stay or death).
- Severity of overall symptoms at Day 0, 1, 5, and 14 is recorded on a 0-10 visual analog scale. Severity of symptoms at Day 5 will be compared first as a categorical analysis (no symptoms vs. symptoms) via Fisher's Exact Chi Square.
 - Second among those with symptoms, the 0-10 visual analog scale severity data will be compared via independent two-sample *t* test. If data are non-normally distributed, then data will be compared via Mann-Whitney U by study arm.

A priori subgroup analyses will include assessment by:

- Confirmed SARS-CoV-2 disease or disease exposure
- Healthcare worker vs. Household contact
- Days from Exposure
- Decile of age
- Sex as a biological variable
- Censored subjects, who became symptomatic before receipt of the first dose of study medicine on D#1, will be separately analyzed and reported.

Handling of withdrawn subjects.

If there is a large lost to follow up / study discontinuation rate, then the primary endpoint for the asymptomatic cohort would have a secondary analysis to assess incidence as a 3-category analysis of: i) no disease, ii) incident disease, or iii) unknown.

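### Section 11.2 claims 80% power for a 40% reduction at a 10% placebo rate, but its own Table 1 needs 771 per arm against 750 randomized and 600 left after 20% loss

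*Combined protocol and SAP*

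**What the plan says.** Section 11.2 plans 750 per arm in each cohort for 90% power, assuming "a two-sided alpha = 0.05 and loss to follow-up up to 20" percent. For the asymptomatic cohort the base case is a "10% transmission rate from COVID-19 cases to close contacts". The Summary (Statistical Assumptions) gives the source of the number: "N=621 sample per arm has 90% power to detect a 50% relative risk reduction", and then "20% dropouts, inflates sample size to n=750 per arm".

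Section 11.2 goes on to say that transmission rates are uncertain and points to Table 1 as evidence that the design can "detect even a smaller (40%) relative reduction in the incidence of COVID 19 with 80% power for transmission rates of at least 10" percent. For a 40% reduction, Table 1 lists these sample sizes per arm:

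| Placebo vs drug | 90% power | 80% power |
|---|---|---|
| 10% vs 6% | 1014 | 771 |
| 12% vs 7.2% | 831 | 632 |
| 15% vs 9% | 648 | 493 |

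Section 11.4 names the primary test: "Incidence of COVID 19 disease by day 14 will be assessed via Fisher's Exact Test".

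**The concern.** The sentence and the table it cites disagree. At the 10% base case the table asks for 771 per arm, more than the 750 to be randomized even if nobody is lost. The plan also allows for up to 20% loss, and 600 per arm falls short of both the 10% row and the 12% row.

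This is the plan's only assurance about an effect smaller than the 50% design target, and it is offered because the event rate is uncertain. Anyone relying on it, including a reader weighing a null result, would take the chance of missing a true 40% reduction at a 10% rate to be at most 20%. With 20% loss it is about 31%. The re-estimation in section 11.3 would not close the gap, because it is powered for a 50% reduction only.

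**Working it through.** **Inputs.** Two-sided alpha 0.05, loss up to 20%, 750 per arm, placebo rate 10% and the Table 1 entries (all section 11.2); 621 per arm for 10% vs 5% at 90% power (Summary and Table 1); Fisher's exact test (section 11.4).

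**1. Reproduce Table 1.** The usual two-proportion formula, with d = p1 − p2 and p̄ the mean of the two rates, is

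n0 = [1.96·√(2p̄(1−p̄)) + z_power·√(p1(1−p1) + p2(1−p2))]² / d²

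and the continuity-corrected size is

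n = (n0/4)·[1 + √(1 + 4/(n0·d))]².

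For 10% vs 6% at 80% power, n0 = 720.9 and n = 770.1, which rounds up to 771. For 10% vs 5% at 90% power, n = 620.4, which rounds up to 621. All twelve entries of Table 1 reproduce in this way. The table is sound; the sentence describing it is not.

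**2. Compare with the numbers available.** Randomized: 750 per arm. After 20% loss: 750 × 0.80 = 600 per arm.

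| 40% reduction | Needed for 80% power | Met by 750? | Met by 600? |
|---|---|---|---|
| 10% vs 6% | 771 | no (short by 21) | no (short by 171) |
| 12% vs 7.2% | 632 | yes | no (short by 32) |
| 15% vs 9% | 493 | yes | yes |

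**3. Power at those sizes.** Three methods: exact Fisher power, by enumerating all outcomes; the continuity-corrected formula behind Table 1; and the uncorrected formula.

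| Comparison | n per arm | Fisher | Corrected | Uncorrected |
|---|---|---|---|---|
| 10% vs 6% | 750 | 79.5% | 78.9% | 81.5% |
| 10% vs 6% | 600 | 69.4% | 68.8% | 72.4% |
| 12% vs 7.2% | 750 | 87.1% | 86.7% | 88.5% |
| 12% vs 7.2% | 600 | 78.4% | 77.8% | 80.7% |
| 15% vs 9% | 600 | 88.0% | 87.6% | 89.3% |
| 10% vs 5% | 600 | 89.7% | 89.0% | 90.9% |

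**4. Where the claim becomes true.** With 600 per arm, 80% power for a 40% reduction needs a placebo rate of about 12.5% by exact Fisher (79.9% at 12.4%, 80.3% at 12.5%), or about 12.6% by Table 1's formula. With 750 per arm and no loss, Table 1's formula gives about 10.3%. Alternatively, with 600 per arm and a 10% placebo rate, the reduction detectable with 80% power is about 45% (10% vs 5.5%: 81.0% by Fisher).

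**5. The loss allowance.** To keep 621 after 20% loss requires 621/0.80 = 776.25, so 777 per arm. The planned 750 is close to 621 × 1.20 = 745.2, which suggests the 20% was added to the required number rather than taken off the randomized number; the documents do not show the step. Either way, 750 tolerates 1 − 621/750 = 17.2% loss.

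**The case against.** The strongest reply concerns importance. The 40% sentence is a sensitivity remark. The 750 per arm rests on a 50% reduction with 90% power, re-estimation targets the same effect, and no test or stopping boundary uses the 40% case. A completed trial's confidence interval, not a pre-trial power statement, shows which effects are excluded. All of that stands, and it limits the consequence.

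It is also fair that 750 against 771 is a trivial gap: half a point of exact power, and the uncorrected formula puts 750 above 80%. The 20% is a ceiling, so the material shortfall appears only as loss approaches it. The 12% row, for example, holds up to 1 − 632/750 = 15.7% loss. But a plan that sizes itself for that loss should not quote a power that ignores it. At 600 per arm, all three methods put 10% vs 6% well below 80%.

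Finally, the SAP clarification of 24 May 2020 keeps participants with missing outcomes in the denominator, so the primary analysis would use 750 per arm rather than 600. This does not restore power. If the 20% lost count as non-events in both arms (an assumption), the rates become 10% × 0.8 = 8% and 6% × 0.8 = 4.8%. Fisher power at 750 per arm is then 68.5%, essentially the same answer.

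**Conclusion.** The concern holds. The statement of 80% power for a 40% reduction at placebo rates from 10% upward is refuted by the table it cites. At the 10% base case, exact power is 79.5% with no loss and about 69% with 20% loss; at 12% with 20% loss it is about 78%. Among Table 1's rows, only 15% supports the claim once the full loss allowance is applied.

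These figures assume equal loss in the two arms, unrelated to outcome, and a single test at two-sided 0.05. They make no allowance for the interim looks in section 11.3 or for removing participants who become symptomatic before the first dose (SAP, I.c).

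The design claim for a 50% reduction is nearly intact: 89.7% at 600 per arm against the stated 90%. The error lies in the plan's description of its power for a smaller effect, with a minor slip in the loss allowance.

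**What to change.** Replace the sentence above Table 1 with one that states the method and the loss, for example: *By exact Fisher power, if 20% of the 750 per arm are lost (600 with outcomes), power for a 40% reduction is about 69% at a 10% placebo rate and 78% at 12%, and reaches 80% from about 12.5%; with no loss it is 79.5% at 10%.* If participants with missing outcomes stay in the denominator as the SAP clarification says, add that the figure at 10% is then about 68.5%, assuming they count as non-events.

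In section 11.2 and in the dropout line of the Summary, either restate the loss allowance as about 17%, or keep 20% and give the power for a 50% reduction as 89.7% with 600 per arm.

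This is a change of text only. It makes the stated power less favourable and adds no participants. Keeping the 40% claim at a 10% rate with 20% loss would instead mean randomizing 771/0.80 = 964 per arm, which the plan's design target does not require.
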